11.7 EXPLORATORY ENDPOINTS

- Young Mania Rating Scale (YMRS) at 10 weeks.
- tDCS Adverse Events Questionnaire (AEQ) at 10 and 20 weeks
- Hamilton Anxiety Rating Scale (HAM-A) change at week 10.

- HDRS-17, MADRS, MADRS-s mean decrease, and remission and response rate at 20 weeks (after open-label) compared to open-label start and baseline.
- Correlation between MADRS and MADRS-s.
- Correlation between adherence to stimulation and HDRS-17/MADRS decrease in the active group at 10 weeks.
- Neuropsychological measure: verbal learning (Rey Auditory Verbal Learning Test (RAVLT) and information processing speed (Symbol-Digit Modalities Test (SDMT)
- Treatment acceptability questionnaire (TAQ) as developed by UEL. There is one form at baseline and another at week 10 and 20.
- The within-patient clinically meaningful improvement as defined as at least -3 points on the HDRS-17 scale. The percentage of subjects for each arm that reaches -3 points or more improvement and also the Cumulative Distribution Function Curves of Change in HDRS-17 Score from Baseline to Primary end-point by arm.

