9 BENEFIT-RISK ANALYSIS

9.1 RISKS

The study device will deliver a maximum of 2 mA tDCS for 30 minutes at a time. Published data has shown conventional sessions to be \leq 40 minutes at \leq 4mA, and the tolerability and dropout rates between sham and active stimulation groups are equal in the literature.

As of August 2021, the most common side effects reported in the literature and from post-market data on Flow FL-100 are:

Side Effect	% of users
Skin irritation, redness	0.80%

Table 4. Common side effects from Flow FL-100

Strong tingling, stinging, or itching	0.14%
Headache	1.1%
Increased tinnitus	0.45%

Most people also experience skin redness at the stimulation site which passes within 30 minutes after the stimulation. Small skin burns are also known from the literature due to the use of tap water instead of physiological saline to wet the stimulation electrodes¹¹. Therefore, Flow is delivered with disposable pre-moistened sponges so that the users do not need to handle saline themselves.

The tDCS studies in participants with MDD have reported mostly consistent adverse events with large studies on healthy participants¹². In addition to this, there have been four studies that have published the appearance of treatment-emergent mania/hypomania (TEM) in eleven cases total¹³. Most cases of TEM have been where tDCS has been combined with antidepressant drugs, which are known to increase the risk of a manic switch¹⁴. As such, a causal relationship has not been determined. The observed cases have also been mild and in general not required any intervention (correspondence with authors). In the internal data from over 3,000 Flow FL-100 users, no instance of TEM has been discovered or reported. In accordance with the recommendation from Antal et al. (2017), participants with a history of bipolar disorder will be excluded from this study due to their increased risk of manic switch. As an additional safety measure, the YMRS will be administered at each follow-up visit.

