12.3 EXCLUSION CRITERIA

Participants who meet any of the following criteria will be excluded from participating in this study:

- 1. Are in a current state of mania, as determined by the YMRS or psychosis, as determined by the MINI.
- 2. Are diagnosed with vitamin or hormonal deficiencies that may mimic mood disorders, as determined by the investigator.
- 3. Are currently receiving any other interventional therapy for MDD other than a stable regimen of antidepressants or psychotherapy as defined in the inclusion criteria.
- 4. Considered to have treatment resistant depression as defined by inadequate clinical response to 2 or more trials of antidepressants at an adequate dose and duration.
- 5. Have a history of electroconvulsive therapy (ECT), transcranial magnetic stimulation (TMS), cranial electrotherapy stimulation (CES), transcranial direct current stimulation (tDCS), deep brain stimulation (DBS), or other brain stimulation.
- 6. Patient answers Yes to Questions 4, 5 or 6 on the Columbia Suicide Severity Rating Scale (C-SSRS) Triage and Risk Identification Screener.
- 7. Any previous hospitilization for suicidal behavior.
- 8. Have chronic severe insomnia (< 4 hours of sleep each night), or depression secondary to chronic insomnia or sleep apnea
- 9. Have any structural lesion (e.g., any structural neurological condition, or more subcortical lesions than would be expected for age or have had a stroke that affects stimulated area or connected areas) or any other clinically significant abnormality that might affect safety, study participation, or confound interpretation of study results, as determined by the investigator.
- 10. Have any implant in the brain (e.g., DBS) or neurocranium, or any other active implantable medical device.
- 11. Have any neurocranial defect.
- 12. Have a history of epilepsy or seizures (including history of withdrawal / provoked seizures).
- 13. Have shrapnel or any ferromagnetic material in the head.
- 14. Have any disorder that would impair the ability to complete the study questionnaires.
- 15. Have been diagnosed with autism spectrum disorder.
- 16. Are actively abusing substances (<1 week prior to enrollment).
- 17. Have a cognitive impairment (including dementia).
- 18. Have a history of mania or psychosis.
- 19. Are currently using any medications that affect cortical excitability (e.g., benzodiazepines, epileptics, etc.).
- 20. Are currently experiencing symptoms of withdrawal from alcohol or benzodiazepines.

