- 21. Have been diagnosed with Parkinsonism or other movement disorder as determined by the investigator to interfere with treatment.
- 22. Have ever taken esketamine / ketamine for treatment of depression.
- 23. Have ever been admitted to hospital for depression.
- 24. Have ever been diagnosed with obsessive-compulsive disorder (OCD) or bipolar type 1 or 2 disorder.
- 25. Is diagnosed with an active primary anxiety disorder, or PTSD, agoraphobia, anorexia or bulimia, panic or personality disorder with active symptoms.
- 26. Have a history of psychosurgery for depression.
- 27. Have any history of myocardial infarction, coronary artery bypass graft (CABG), coronary heart failure (CHF), or history of other cardiac issues.
- 28. Are currently experiencing or have a history of intractable migraines.
- 29. Are a chronic tobacco smoker, as defined by smoking by smoking >100 cigarettes (including hand-rolled cigarettes, cigars, cigarillos, etc.) in their life-time and have smoked every day for the last 7 days.

- 30. If female and of child-bearing potential, currently pregnant or breastfeeding or planning to become pregnant or breastfeed any time during the study.
- 31. Are currently a prisoner.
- 32. Are participating concurrently in another clinical investigation or have participated in a clinical investigation within the last 90 days or intend to Participate in another clinical investigation during the study, and where the participation in the other investigation might interfere with the results of this trial as deemed by the PI.
- 33. Have any medical condition or other circumstances, in the judgment of the investigator, that might interfere with the ability to complete follow-up visits and the self-reported MADRS-s in the app.
- 34. Have any condition which, in the judgment of the Investigator, would preclude adequate evaluation of the device's safety and performance.
- 35. A Subject who meets any of the exclusion criteria during study participation will be discontinued from the study

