Columbia Suicide Severity Rating Scale (C-SSRS) - ClinRo

The Columbia Suicide Severity Rating Scale, or C-SSRS, is a rating scale to evaluate suicide risk. The scale identifies specific behaviors which may be indicative of an individual's intent to kill oneself.

Hamilton Anxiety Rating Scale (HAM-A) - ClinRo

The HAM-A was one of the first rating scales developed to measure the severity of anxiety symptoms and is still widely used today in both clinical and research settings. The scale consists of 14 items, each defined by a series of symptoms, and measures both psychic anxiety (mental agitation and psychological distress) and somatic anxiety (physical complaints related to anxiety).

Young Mania Rating Scale (YMRS) - ClinRo

The Young Mania Rating Scale (YMRS) is one of the most frequently utilized rating scales to assess manic symptoms. The scale has 11 items and is based on the patient's subjective report of his or her clinical condition over the previous 48 hours.

Rey Auditory Verbal Learning Test (RAVLT) - ClinRo

The Rey Auditory Verbal Learning Test (RAVLT) is a neuropsychological assessment designed to evaluate verbal memory in patients, 16 years of age and older. The RAVLT can be used to evaluate the nature and severity of memory dysfunction and to track changes in memory function over time.

Symbol-Digit Modalities Test (SDMT) - PRO

The Symbol Digit Modalities Test (SDMT) detects cognitive impairment. It is a way for clinicians to screen for organic cerebral dysfunction in both children (eight years and older) and adults. The SDMT is brief, easy to administer, and has demonstrated sensitivity in detecting not only the presence of brain damage, but also changes in cognitive functioning over time and in response to treatment.

Treatment Acceptability Questionnaire (TAQ) - PRO

TAQ is a questionnaire for probing how acceptable participants of tDCS clinical trial think the treatment is. At baseline it measures participant's expectations about the trial, e.g., treatment outcome, effort needed, ethics, etc., and then follow-up on these expectations at the end of the trial.

tDCS Adverse Events Questionnaire (AEQ) - PRO

AEQ is a specialized questionnaire developed to capture the adverse events during tDCS trials.

EQ-5D-3L - PRO

The EQ-5D-3L is a standardized measure of health-related quality of life.

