22.8 SECONDARY EFFECTIVENESS ENDPOINTS

Secondary effectiveness endpoints will be analyzed descriptively.

For continuous variables (CONT), results will be summarized with the numbers of observations, means, standard deviation, median, minimums and maximums. Differences between the two groups, where specified, will be summarized with the differences of the two means, and 95% confidence intervals for the difference between the means. These calculations will be done under the assumption that data for the two groups are independent and approximately normally distributed. The confidence interval for the difference of two means will be calculated under the assumption of unequal variances. If the asymptotic assumptions fail, then nonparametric summary statistics (medians, 25th and 75th percentile) may be displayed as an alternative.

For binary variables (BIN), results will be summarized with patient counts, percentages/rates. Differences between the two groups, where specified, will be summarized with the difference in percent and the Newcombe score 95% confidence interval for the difference of two percentages.

For correlation analysis, Spearman correlation will be used to assess the association between two continuous variables. The correlation coefficient and the 95% confidence intervals will be reported.

CONFIDENTIAL Page **61** of **69**

There are three secondary endpoints controlled multiplicity (see below):

- The mean change in points for MADRS score from baseline to Week 10. This will be evaluated using the same statistical methodology as the primary endpoint.
- Clinical Response will be analyzed as a responder endpoint. Clinical Response is defined as a >50% reduction from the baseline HDRS-17 or MADRS score, MADRS-s at Week 10.
- Remission will be analyzed as a responder endpoint where remission is defined as an HDRS-17 score ≤7 or a MADRS score ≤10). The endpoint will be tested using a two-group large-sample normal approximation test of proportions with a one-sided 0.025 considered significant.
- Quality of life improvement as measured by EQ-5D-3L in the active compared to sham arm at week 10 compared to baseline.

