22.9 EXPLORATORY ENDPOINTS

The following list of secondary endpoints will be analyzed using the mITT population and will be summarized based on the type of data: Continuous (CONT), Binary (BIN) or Correlation (CORR):

- Montgomery–Åsberg Depression Rating Scale (MADRS) response rate at all follow-up time points (CONT)
- Montgomery–Åsberg Depression Rating Scale Self-report (MADRS-s) scores of the two arms (response and remission rates) at all time points (CONT)
- Hamilton Anxiety Rating Scale (HAM-A) at all time points (CONT)
- Young Mania Rating Scale (YMRS) at all time points (CONT)
- tDCS Adverse Events Questionnaire (AEQ) at 10 and 20 weeks (CONT)
- HDRS-17 (CONT), MADRS (CONT), MADRS-s mean decrease (CONT), remission (BIN), and response rate (BIN) at 6 weeks comparison between groups.
- HDRS-17 (CONT), MADRS (CONT), MADRS-s (CONT) at 20 weeks (after open-label)
- Correlation between MADRS and MADRS-s. (CORR)
- Correlation between the percent of sessions using the FLOW FL-100 and HDRS-17/MADRS decrease in the active group at 10 weeks.
- The within-patient clinically meaningful improvement as defined as at least -3 points on the HDRS-17 scale. The percentage of subjects for each arm that reaches -3 points or more improvement and also the Cumulative Distribution Function Curves of Change in HDRS-17 Score from Baseline to Primary end-point by arm.

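### The YMRS endpoint is Week 10 only in 11.7 but all time points in 22.9, and neither shows how many participants per arm ever had mania by YMRS

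*Protocol*

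**What the plan says.** Section 9.1 gives the reason for measuring YMRS. Four tDCS studies have "published the appearance of treatment-emergent mania/hypomania (TEM) in eleven cases total", and as an added safeguard "the YMRS will be administered at each follow-up visit". Sections 13.3 to 13.5 schedule it at Weeks 1, 4, 7, 10 and 20, and 13.8 adds unscheduled visits. The early-termination visit in 15.4, which repeats the Week 10 and Week 20 data, is optional.

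The endpoint appears in two forms. Section 11.7 and the synopsis have "Young Mania Rating Scale (YMRS) at 10 weeks", with no summary measure. Section 22.9 has "Young Mania Rating Scale (YMRS) at all time points (CONT", where the code marks a continuous variable, analysed in the mITT set. For such variables 22.8 says "results will be summarized with the numbers of observations, means, standard deviation, median, minimums and maximums".

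Two eligibility items bear on who is still rated at Week 10. Exclusion 1 covers those who "Are in a current state of mania, as determined by the YMRS or psychosis, as determined by the MINI". Item 35 extends it through the trial: "A Subject who meets any of the exclusion criteria during study participation will be discontinued from the study". Section 15.6 keeps in the analysis whatever was collected before discontinuation. Section 22.3.2 assigns all safety and tolerability summaries to the As Treated set.

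**The concern.** Treatment-emergent mania is a rare event that a participant either has or does not have. A score taken only at Week 10 is available mainly for those who did not have it earlier, because those who did are discontinued under item 35. Section 14 adds that the scale rests on the patient's "subjective report of his or her clinical condition over the previous 48 hours", so an episode that has resolved leaves no trace at Week 10 either. A Week 10 summary that looks the same in both arms could then be read as showing no mania signal, although participants in one arm had switched and left. The protocol's second form of the endpoint, in 22.9, does not have this gap to the same degree, but it describes scores at visits and does not count people.

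**Working it through.** The protocol gives no figure for YMRS or for the frequency of mania, so there is none to reproduce. The only input taken from it is the arm size: 270 randomised 1:1, or 135 per arm. Case counts, onset patterns and score excesses below are assumptions.

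1. **Who has a Week 10 score.** A participant whose YMRS shows mania at Week 1, 4 or 7 meets exclusion 1 and is discontinued under item 35. Any later YMRS comes from an optional early-termination visit and is not a scheduled Week 10 score. Under the 11.7 wording that participant is normally absent.

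2. **What share of cases this removes.** Let F(t) be the proportion of onsets by week t, and suppose each case is detected and discontinued at the next scheduled visit. The share gone before Week 10 is F(7):
   - uniform onset: 7/10 = 70%;
   - onset proportional to sessions: (5 × 3 + 3 × 4)/36 = 27/36 = 75%;
   - back-loaded onset, F(t) = (t/10)²: 0.7² = 49%.

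3. **How far a mean moves.** With k cases among n participants, each d points above the rest, the arm mean shifts by k × d/n.
   - k = 2, d = 18, n = 135: 2 × 18/135 = 0.27 points.
   - k = 3: 3 × 18/135 = 0.40 points.
   - All cases discontinued before Week 10: 0 at Week 10.
   - As a count, k = 2 gives 2/135 = 1.5%.

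   Over a wider range, with incidence p of 1% to 5% and d of 10 to 20, the shift with every case kept is p × d, from 0.01 × 10 = 0.10 to 0.05 × 20 = 1.0. At Week 10 after removal under uniform onset it is 0.3 × p × d/(1 − 0.7 × p), from 0.03/0.993 = 0.03 to 0.30/0.965 = 0.31.

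4. **What 22.9 recovers.** A detecting score at Week 1, 4 or 7 is kept by 15.6 and enters that visit's summary, where the maximum would show it. A maximum shows one worst score, so it cannot tell one affected participant from three. Cases first seen at different visits are not added up. Scores from unscheduled and early-termination visits are collected, but the protocol gives them no place in a by-visit summary.

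5. **Which analysis set.** YMRS is described in 9.1 as a safety measure, and 22.3.2 puts all safety summaries in the As Treated set. Section 22.9 puts YMRS in mITT. By 22.3.3 exclusions from mITT should be few, so the numerical difference is probably small, but the two sections do not agree.

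**The case against.** The strongest reply is that the planned analysis does keep the cases. Section 22.9 covers every time point, its summaries include the maximum, and 15.6 retains scores from discontinued participants. This stands. A reader might infer that the trial's mania analysis as a whole is computed without the cases it is meant to find, or that it rests on a Week 10 mean alone. The documents do not support that. Section 11.7 names no mean, and the selection applies to the Week 10 wording in 11.7 and the synopsis, not to 22.9.

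A second reply is that mania can be counted through adverse events. It is not named among the anticipated events in 19.1, so it could be recorded individually. Section 22.14 then gives per-subject incidence by group in the As Treated set and a listing for those discontinued early. This largely stands, with one limit. Acute mood change is on the anticipated list, and section 19 routes the frequency and severity of anticipated events to the AEQ, which is scheduled after baseline only at Weeks 10 and 20 and at early termination. Section 9.1 describes the published cases as mild, so a mild switch could be recorded by either route.

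Third, the endpoint is exploratory with no safety hypothesis attached, and 9.1 reports no such case among more than 3,000 users of the device. Extra tables and thresholds are also often left to the SAP, which was not available for this review. The lack of a threshold is therefore not counted as a fault here. The disagreements over time point and analysis set are in the protocol itself.

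Finally, an ever-case count shares the 48-hour limit: an episode that starts and ends between visits is missed. It also needs a YMRS criterion, and the protocol states none for exclusion 1. Both points stand.

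**Conclusion.** The point holds in a limited form. Sections 11.7 and 22.9 give different time points for the same endpoint and must be reconciled. Read literally, the Week 10 wording selectively omits participants discontinued for mania: 49% to 75% of cases under the three assumed onset patterns. The by-visit summaries in 22.9 retain the detecting scores, and adverse-event reporting may capture cases as well, but neither provides a count by arm of participants whose YMRS ever indicated mania. The shifts of 0.27 and 0.40 points are illustrations that rest on assumed case counts and an assumed 18-point excess. They show how little a mean responds to a rare event and do not predict this trial's data. The change is a cheap improvement to an exploratory endpoint and does not affect the primary analysis.

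**What to change.** - Align 11.7 and the synopsis with 22.9, so that one YMRS endpoint with one set of time points is stated throughout.
- Add, by arm in the As Treated set, the distribution of each participant's maximum post-baseline YMRS up to Week 10, taken over all scheduled, unscheduled and early-termination visits.
- In the same table, give the number and percentage of participants who ever met the YMRS criterion applied for exclusion 1. Record that criterion in writing before unblinding.
- Keep the by-visit summaries as supportive, and report Weeks 10 to 20 separately, since the sham arm is then offered active stimulation.

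The cost is one extra table from scores already collected, with no new assessment. Episodes that resolve between visits would still be missed. No cut-off is proposed here, and no change to the discontinuation rule.

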12 SELECTION OF STUDY POPULATION

12.1 PARTICIPANT RECRUITMENT

Participants in this study will be recruited via the Flow Neuroscience website, email lists, and online marketing. Potential participants will be directed to a pres-creening form hosted by Curebase, they will then be required to sign up/register with the Curebase platform to complete a pre-screening survey. This information will primarily be used to screen potential participants for eligibility. Users will be given general information about the trial, and that is it will be blinded.

Participants who seem to meet preliminary eligibility will have a virtual pre-screening visit with a Curebase coordinator prior to being sent to a site investigator for informed consent and further screening procedures. Participants must meet all the following inclusion criteria and none of the exclusion criteria. The investigator maintains exclusive responsibility for the inclusion and exclusion of any potential study participant.

12.2 INCLUSION CRITERIA

To be eligible to participate in this study, participants must meet all the following criteria:

- 1. Be ≥18 years.
- Have a diagnosis of Unipolar MDD with a current depressive episode as defined by the diagnostic criteria in the Diagnostic and statistical manual of mental disorders – 5th edition (DSM-V
- 3. Have a Hamilton Depression Rating Score (HDRS-17) of \geq 16.
- 4. For 6 weeks prior to enrollment, are either:
 - a. not taking antidepressant medication or:

- b. are taking a stable antidepressant regimen with a stable medication source and agree to continue the same regimen throughout study participation
- 5. If in psychotherapy, have maintained stable psychotherapy for at least 6 weeks prior to enrollment.
- 6. Have access to a stable internet connection through which the treatment will be received.
- 7. Have access to a smartphone or other device running Android 5.0+ or iPhone Operating System (iOS) 12+ (e.g., reasonably new iPhone/iPad or Android phone), used to using the device in their everyday life, and can capably use the study application on the device, as determined by the investigator.
- 8. Are currently living in England/Wales (UK) or Texas (US).
- 9. Subject is currently under the care of a psychiatrist or a primary care physician, agrees to be evaluated at regular intervals by a psychiatrist or primary care physician for the duration of study participation, and agrees to promptly inform the study staff of any change of psychiatric or mental health providers during study participation.
- 10. Subject agrees to allow any and all forms of communication between the investigators/study staff and any healthcare provider who currently provides and/or has provided service to the patient/subject within at least two years of study enrollment.
- 11. Subject agrees to provide the name and verifiable contact information (email and mailing addresses, mobile and land-line phone numbers, as applicable) of at least two persons ≥ age 18 who reside within a 60-minute drive of the patient's residence and whom the research staff is at liberty to contact, as they deem necessary, for the duration of study participation.
- 12. Be able to give voluntary, written informed consent to participate and have signed an Informed Consent Form specific to this study.
- 13. Be willing and able to comply with all study procedures.
- 14. Subject agrees to meet all of the inclusion criteria throughout their participation in the study. Otherwise, the subject will be discontinued from the study.
- 15. Subject agrees to a Safety/Suicide Risk Management Protocol, which is intended to reduce the reduce the risk of suicide during study participation.

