14. Subject agrees to meet all of the inclusion criteria throughout their participation in the study. Otherwise, the subject will be discontinued from the study.15. Subject agrees to a Safety/Suicide Risk Management Protocol, which is intended to reduce the reduce the risk of suicide during study participation.Participants who meet any of the following criteria will be excluded from participating in this study:1. Are in a current state of mania, as determined by the YMRS or psychosis, as determined by the MINI.2. Are diagnosed with vitamin or hormonal deficiencies that may mimic mood disorders, as determined by the investigator.3. Are currently receiving any other interventional therapy for MDD other than a stable regimen of antidepressants or psychotherapy as defined in the inclusion criteria.4. Considered to have treatment resistant depression as defined by inadequate clinical response to 2 or more		13. Be willing and able to comply with all study
Exclusion Criteriathroughout their participation in the study. Otherwise, the subject will be discontinued from the study.15. Subject agrees to a Safety/Suicide Risk Management Protocol, which is intended to reduce the reduce the risk of suicide during study participation.Participants who meet any of the following criteria will be excluded from participating in this study:1. Are in a current state of mania, as determined by the YMRS or psychosis, as determined by the MINI.2. Are diagnosed with vitamin or hormonal deficiencies that may mimic mood disorders, as determined by the investigator.3. Are currently receiving any other interventional therapy for MDD other than a stable regimen of antidepressants or psychotherapy as defined in the inclusion criteria.4. Considered to have treatment resistant depression as defined by inadequate clinical response to 2 or more		

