11.4 OPEN LABEL PHASE

After the completion of the blinded treatment phase all participants will be offered to continue the treatment. Members of the sham group will be offered to restart the treatment with active stimulation, while members of the active group will be offered to continue maintenance treatment for 10 more weeks at 3 sessions per week.

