11.6 SECONDARY ENDPOINTS

- Arm difference in HDRS-17 response and remission rate at week 10.
- Arm difference in MADRS average score change, and response and remission rate at week 10.
- Arm difference in MADRS-s average score change, and response and remission rate at week 10.
- Quality of life improvement as measured by EQ-5D-3L in the active compared to sham arm at week 10.

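### Criterion 14 makes HDRS-17 of at least 16 a continuing condition with mandatory discontinuation, so read literally it removes participants who improve before week 10

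*Protocol*

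**What the plan says.** Section 12.2, criterion 14, reads: "Subject agrees to meet all of the inclusion criteria throughout their participation in the study. Otherwise, the subject will be discontinued from the study". The study summary (section 6) carries the same rule: "Subject agrees to meet all of the inclusion criteria throughout their participation in the study".

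The severity threshold is criterion 3, "Have a Hamilton Depression Rating Score (HDRS-17) of" at least 16, with no reference to screening or baseline. Criterion 2, a current depressive episode, is equally open-ended. Criterion 4, by contrast, fixes its time frame: "For 6 weeks prior to enrollment, are either". Criterion 5 is tied to the same six weeks.

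Table 1 and sections 13.3 and 13.4 schedule HDRS-17 at weeks 1, 4, 7 and 10. Section 11.6 lists as a secondary endpoint "Arm difference in HDRS-17 response and remission rate at week 10", and section 22.8 states that "remission is defined as an HDRS-17 score ≤7 or a MADRS score ≤10", with response a drop of more than 50% from baseline. Section 11.4 says: "After the completion of the blinded treatment phase all participants will be offered to continue the treatment". Section 11.7 adds "remission and response rate at 20 weeks (after open-label) compared to open-label start and baseline".

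**The concern.** The second sentence of criterion 14 is mandatory and leaves the investigator no discretion. Because it covers every inclusion criterion, it covers the minimum HDRS-17 score, which an effective treatment is meant to bring down. A site or monitor following the text would have to discontinue a participant because the score had fallen below 16.

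At stake are scheduled week-10 ratings of early improvers, and possibly open-label treatment and week-20 ratings of people who first fall below 16 at week 10. Under section 15.4 a withdrawn participant's device is disabled, and the only further assessment is an optional early termination visit held around the time of withdrawal rather than at week 10.

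**Working it through.** The check compares thresholds and visit timing, using the protocol's own figures.

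**1. Which improvements breach criterion 3 (HDRS-17 of at least 16)?**
- Remission: a score of 7 or less is always below 16, so every HDRS-17 remitter breaches it.
- Response, a drop of more than 50%: the score is below baseline/2. With baseline 32, 32/2 = 16, so a responder scores 15 or less. With baseline 33, 33/2 = 16.5, so a responder could still score 16. Every HDRS-17 responder with baseline 16 to 32 therefore breaches it.
- The exploratory 3-point improvement (section 11.7): 16 − 3 = 13, 17 − 3 = 14 and 18 − 3 = 15 are all below 16, while 19 − 3 = 16 still qualifies. Anyone with baseline 16 to 18 who reaches this improvement breaches it.

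**2. When would the breach be seen, and what does it conflict with?**

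| First HDRS-17 below 16 | Consequence if criterion 14 is applied literally | Conflict |
|---|---|---|
| Week 1, 4 or 7 | Discontinued before week 10; optional early termination visit only | Week-10 response and remission (11.6, 22.8) |
| Week 10 | Week-10 rating already made and counted | None at week 10; with 11.4 and the week-20 endpoints (11.7) only if criterion 14 continues into the open-label phase |

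The offer in 11.4 follows completion of the blinded phase. Someone discontinued at week 1, 4 or 7 never completes it, so 11.4 itself is contradicted only in the second row.

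**3. Does criterion 2 add a trigger?** Table 1 places the MDD diagnostic assessment and the MINI in the pre-treatment column only, and sections 13.3 to 13.5 and 13.8 do not repeat them. The wording gap is the same, but episode status is not re-assessed, so there is no practical trigger.

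**4. Treatment forgone under literal enforcement.** The protocol's own total reproduces from Table 2: 3 × 5 + 7 × 3 = 36 blinded sessions.
- Stopped after week 1: 5 done, 36 − 5 = 31 forgone.
- Stopped after week 4: 15 + 3 = 18 done, 36 − 18 = 18 forgone.
- Stopped after week 7: 15 + 4 × 3 = 27 done, 36 − 27 = 9 forgone.
- Open-label phase (Table 3), if stopped at week 10: 10 × 3 = 30 for the active arm, or 3 × 5 + 7 × 3 = 36 for the former sham arm.

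**5. Sample size.** The inputs in section 22.2 are a difference of 3.2, SDs of 7.1 and 7.9, one-sided 0.025, and 20% attrition (216/0.80 = 270). None depends on criterion 14, so a wording change alters no figure there.

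**The case against.** The strongest reply is that the rule was never meant this way. The list opens as conditions of eligibility. Section 13.1 uses HDRS-17 in the screening call that confirms eligibility and holds the only listed eligibility review. Section 22.4 places randomization after the criteria have been met. The only HDRS-17 trigger in section 15.2 is a 30% increase. A participant can agree to keep a medication regimen but cannot sensibly agree to stay depressed. Exclusion 35 shows similarly loose drafting: read with exclusion 5 (any history of tDCS), it would discontinue active-arm participants for receiving the study treatment.

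Most of this stands as evidence of intent, and sites would probably not enforce the rule against improvers. It does not supply an exemption: the order to discontinue is unqualified, and silence about improvement in sections 15.2 and 15.4 does not override it.

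A second reply also stands. Under section 13.9 participation ends at week 10 unless the person consents to and enrols in the open-label portion. It can be argued that criterion 14 does not reach across that step. The same section has open-label participants completing the trial at 20 weeks, so the opposite reading is also open.

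A reader might infer that the trial will in fact lose its responders and so bias the primary comparison. The documents do not support that. Section 15.6 keeps data already collected, and section 22.5.1 allows for missing week-10 values through the MMRM or multiple imputation. Nor does the rule make week-10 remission unobservable, since anyone first below 16 at that visit is still scored.

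**Conclusion.** The inconsistency is real but minor. As written, criterion 14 discontinues participants whose HDRS-17 falls below 16 at week 1, 4 or 7, which cannot be reconciled with measuring response and remission at week 10. The conflict with the open-label offer and the week-20 endpoints is conditional: it concerns people first below 16 at week 10 and requires criterion 14 to continue past the step in section 13.9.

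This rests on a literal reading and on treating discontinuation under criterion 14 like a withdrawal under section 15.4. The session counts describe literal enforcement, not an expected loss. A reader might go on to infer that removals would exceed the 20% attrition allowance or fall unequally between the arms. The protocol gives no baseline mean and no expected change in the sham arm, so neither the number affected nor its split by arm can be derived.

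**What to change.** - Limit criterion 14, in section 12.2 and the study summary, to a named list of continuing criteria, for example 4b, 6 to 11, 13 and 15, for the sponsor to confirm.
- Mark criteria 2 and 3 as assessed at screening or baseline only.
- State that an HDRS-17 score below 16 does not end treatment, scheduled assessments or the open-label offer.
- In exclusion 35 (section 12.3 and the study summary), state that history-type exclusions such as exclusion 5 refer to the period before enrolment.

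The cost is one wording amendment submitted under section 23.3. It needs no extra participants, visits or analyses.
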